7.3.3.3. Multiple Imputation

A fully conditional specification method (van Buuren 2007) that assumes the existence of a joint distribution for all variables will be used to impute missing 7-day average WI-NRS scores at each visit. A regression model, including treatment group, stratification factors, baseline WI-NRS score, and WI-NRS scores for each scheduled postbaseline visit up to Week 12, will be specified for the fully conditional specification method. The imputation will be repeated 30 times to generate corresponding complete data sets in order to reflect the uncertainty around the true values. Random seeds of "18424319" for the INCB 18424-319 study and "18424320" for the INCB 18424-320 study will be used for the multiple imputation. After the missing values are imputed, the binary variables will be derived based on the definition. The CMH test similar to that for the primary analysis will be applied to each imputed dataset for comparison at Week 12, and the results will then be combined for inference using Rubin's rule.

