3.3. Sample Size Considerations

Approximately 180 participants will be randomized 1:1 to ruxolitinib 1.5% cream BID or vehicle cream BID. The sample size calculation is based on the Fisher exact test for the primary efficacy endpoint, which is the proportion of participants with WI-NRS4 response at Week 12. The mechanism of stopping the itch-scratch cycle and reducing the pruritus are similar between PN and AD. Additionally, based on the results from the following nemolizumab studies: a Phase 2 study in AD (Silverberg et al 2020), a Phase 2 study in PN (Galderma 2021), and a Phase 3 study in PN (Galderma 2022), the improvement in WI-NRS is not substantially different between AD and PN. Therefore, the results from 2 Phase 3 studies (INCB 18424-303 and INCB 18424-304) of ruxolitinib cream in the treatment of AD are used to build the assumptions of the proportion of participants with WI-NRS4 response, which are 50% for ruxolitinib 1.5% cream BID and 25% for vehicle cream BID. Using a 2-sided $\alpha = 0.05$, the sample size based on the current assumption will have > 90% power to detect a difference between ruxolitinib cream and vehicle cream. In addition, the assumptions and powers for key secondary endpoints are provided in Table 2.

Table 2: Powering for Key Secondary Endpoints

Variables	Response Rates in Ruxolitinib 1.5% BID	Response Rates in Vehicle BID	Power: 1.5% BID vs Vehicle BID
WI-NRS4 response at Week 4	40%	15%	> 90%
Overall-TS (WI-NRS4 response and IGA-CPG-S-TS) at Week 12	30%	10%	> 90%
IGA-CPG-S-TS at Week 12	40%	20%	80%
WI-NRS4 response on Day 7	30%	10%	> 90%

Note: Based on Fisher's exact test, 2-sided α = 0.05.

In addition to providing adequate power for efficacy variables, the sample size is determined to provide an adequate database for safety evaluations.

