7.2. Efficacy Measures

7.2.1. Worst-Itch Numeric Rating Scale

The WI-NRS is a PRO comprised of a single item rated on a scale from 0 ("No itch") to 10 ("Worst imaginable itch"). Each evening beginning on the day of screening through Week 52 or ET, the participant will assess their worst level of PN-related itch during the past 24 hours on a scale of 0 to 10 in an eDiary.

The WI-NRS score for baseline will be determined by averaging the 7 daily WI-NRS scores before Day 1 (ie, Days -7 to -1) for all by-visit summaries. The by-visit WI-NRS score for postbaseline visits will be determined by averaging the 7 daily WI-NRS scores before the visit day. If 4 or more daily scores are missing (out of the 7), the WI-NRS score at the visit will be set to missing. For all daily WI-NRS-related analyses, baseline will be defined as the last available daily WI-NRS score during the last week prior to Day 1 (ie, Days -7 to -1).

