7.3. Analysis of the Primary Efficacy Parameter

7.3.1. Primary Efficacy Analysis

The primary analysis will be based on the ITT Population in the DBVC period. A summary of the primary endpoint analysis is provided in Table 5.

Table 5: Summary of Primary Analysis

Parameter	Definition	
Treatment	Ruxolitinib 1.5% cream compared with vehicle cream	
Population	ITT Population	
Variable	WI-NRS4 response at Week 12	
Population-level summary	WI-NRS4 response rate difference with 95% CI	

Note: Participants with missing Week 12 data for any reason, including treatment discontinuation (due to development of AD lesions or any other cause), will be defined as nonresponders. No rescue therapy is allowed in this study.

The WI-NRS score at each postbaseline visit (ie, the by-visit WI-NRS score), will be determined by averaging the 7 daily NRS scores before the visit day. If 4 or more daily scores are missing (out of the 7), the WI-NRS score at the visit will be set to missing. Missing WI-NRS scores at each postbaseline visit will be imputed as nonresponders for the primary analysis. The baseline for the by-visit WI-NRS score will be determined by averaging the 7 daily NRS scores before Day 1 (ie, Day -7 to Day -1). The proportion of participants with a WI-NRS4 response, defined as achieving a \geq 4-point improvement in the by-visit WI-NRS score from baseline, will be summarized by treatment group and visit.

The primary hypothesis specified in Section 7.1 will be tested at a 2-sided $\alpha = 0.05$ level using a CMH test stratified by IGA-CPG-S score (2 or \geq 3) and geographic region (North America or outside of North America). The p-value and stratum-adjusted WI-NRS4 response rate difference with the 95% CI will be provided. An overall odds ratio will also be provided with the 95% CI.

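### The multiple-imputation check of the primary endpoint leaves out the itch diary recorded after Week 8, so its missing-at-random assumption is less credible than the collected data allow

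*SAP*

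**What the plan says.** SAP 7.3.3.3 plans a sensitivity analysis in which a fully conditional specification method "will be used to impute missing 7-day average WI-NRS scores at each visit". The predictors are given as "A regression model, including treatment group, stratification factors, baseline WI-NRS score, and WI-NRS scores for each scheduled postbaseline visit up to Week 12". Protocol 10.4.1 describes the same model. The scheduled postbaseline visits up to Week 12 are Weeks 2, 4, 8 and 12 (Protocol Table 3).

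The underlying data are denser. SAP 7.2.1 states: "Each evening beginning on the day of screening through Week 52 or ET, the participant will assess their worst level of PN-related itch". Protocol 8.3.1 ends the diary at Week 52 or treatment discontinuation. A visit score is the mean of the seven preceding daily scores, with this rule in SAP 7.3.1: "If 4 or more daily scores are missing (out of the 7), the WI-NRS score at the visit will be set to missing". One to three observed entries in the last week are therefore set aside.

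Four other parts of the plan bear on the point:
- The primary analysis counts a missing Week 12 score as nonresponse (SAP 7.3.1).
- A tipping point analysis runs from the least to the most favourable assignment of missing responses (SAP 7.3.3.4).
- The imputation for the Day 7 key secondary endpoint does use daily scores as predictors (SAP 7.4).
- An ET1 visit is planned for anyone who stops study cream before Week 12 (Protocol 8.8). The SAP text available does not say whether its seven-day average enters the imputation.

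**The concern.** Multiple imputation is valid here if missingness at Week 12 is unrelated to the missing score, given the variables in the model. With visit averages only, a participant whose last diary entry is at the end of Week 11 is imputed from Week 8 and earlier, and the 21 evenings of Weeks 9 to 11 count for nothing. If stopping depends on what happened in those weeks, the data may be missing at random given the diary but not given the model as written.

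The protocol contains a route to this. Under Protocol 7.1.1, worsening PN that needs a prohibited medication, or that takes the treated area above 20% BSA, leads to discontinuation, and the diary then stops. Stopping because of improvement is not a planned route before Week 12: interruption for clear skin without itch is confined to the open-label period (Protocol 6.5). Late worsening is thus plausible, although worsening by extent is not the same as worsening itch, and people stop for other reasons.

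What is at stake is how informative this check is. The tipping point analysis shows how extreme an assumption must be to change the conclusion. The imputation is meant to show what is plausible.

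**Working it through.** **The plan's own figure.** SAP 3.3: "Approximately 180 participants will be randomized 1:1 to ruxolitinib 1.5% cream BID or vehicle cream BID", with response rates "which are 50% for ruxolitinib 1.5% cream BID and 25% for vehicle cream BID", so that "the sample size based on the current assumption will have > 90% power to detect a difference between ruxolitinib cream and vehicle cream". Exact enumeration of the Fisher test at 90 per arm, 50% against 25%, two-sided 0.05, gives 92.3%. The stated power reproduces.

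**Diary use.** Four visits × 7 days = 28 of 12 × 7 = 84 postbaseline evenings enter the model. For someone missing Week 12 it is 3 × 7 = 21.

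**Simulation.** From the documents: Week 12 response about 50% and 25%, visits at Weeks 2, 4 and 8, response as a reduction of at least 4 points. Assumed, because the documents are silent: dropout of 5%, 10% or 20%, occurring after Week 11; SD of change 2.6, half of its variance between participants; weekly autocorrelation 0.85. There were 100,000 simulated participants per arm. Missing Week 12 scores were imputed by Bayesian linear regression on treatment, baseline and Weeks 2, 4 and 8, then again with Weeks 9, 10 and 11 added. Strata were omitted and 5 imputations used, since only bias was measured.

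Response among participants missing Week 12, at 10% dropout (ruxolitinib / vehicle):

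| Dropout driven by | True | As written | Weeks 9–11 added |
|---|---|---|---|
| Worsening after Week 8 | 38% / 16% | 63% / 36% | 39% / 16% |
| Improvement after Week 8 | 63% / 35% | 38% / 16% | 62% / 35% |
| Nothing (random) | 51% / 25% | 50% / 25% | 51% / 25% |
| Week 8 score | 16% / 6% | 16% / 5% | 16% / 5% |

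**Effect on each arm.** Bias in an arm's rate = fraction missing × (imputed − true response among the missing). For late worsening at 10%:
- Ruxolitinib: 0.096 × (0.633 − 0.384) = +2.4 points.
- Vehicle: 0.103 × (0.363 − 0.164) = +2.0 points.
- Difference between arms: about +0.4 points before rounding of the arm figures (simulated difference 25.47 against 25.12).

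The same formula in the other settings, in points:

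| Pattern | Dropout | Ruxolitinib | Vehicle | Difference |
|---|---|---|---|---|
| Late worsening | 5% | +1.3 | +1.1 | +0.2 |
| Late worsening | 20% | +4.6 | +4.0 | +0.6 |
| Late improvement | 5% | −1.3 | −1.0 | −0.3 |
| Late improvement | 10% | −2.5 | −1.9 | −0.6 |
| Late improvement | 20% | −4.7 | −3.5 | −1.3 |

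**One arm only.** If the pattern occurs in a single arm, nothing cancels, and that arm's bias carries into the difference: about 1 to 5 points. Late worsening on ruxolitinib alone inflates the difference; on vehicle alone it shrinks it.

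**A second set of assumptions.** A separate simulation used 90 per arm, true rates about 52% and 27%, daily noise SD 1 and weekly autocorrelation 0.6 to 0.8, with dropout driven by recent itch.
- With about 16% missing on ruxolitinib against 4–5% on vehicle, the model as written overstated the difference by 0.9 to 1.6 points. With about 2% against 22% it understated it by the same amount. Adding the weekly averages left a bias within 0.1 point.
- Residual variance of the Week 12 score fell from 1.25–2.54 to 0.61–0.77. The extra weeks therefore sharpen the imputation as well as reducing bias.

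**The case against.** A visit-based imputation model is a legitimate prespecified choice. It follows the protocol and was added at a health authority's request (Protocol Appendix C, Amendment 1). It is one sensitivity analysis beside a longitudinal logistic model, a per-protocol analysis and a tipping point analysis. The tipping point range contains any error this imputation could make, and it does not rely on missing at random. Against a planned difference of 25 points, the standard error at 90 per arm is √(0.5 × 0.5/90 + 0.25 × 0.75/90) = 7.0 points, so a shift below 1 point is small. An ET1 score, if mapped into the model, would reveal some late worsening. Participants who stop by Week 8 have no later diary to add.

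Most of this stands, and it rules out three stronger readings that a reader might draw:
- **Imputed participants are called responders too often.** This is true only if dropout follows worsening after Week 8. Under random or Week 8-driven dropout there is essentially no bias, and after late improvement it reverses. The documents do not say which applies.
- **This is the only imputation-based check.** The tipping point analysis also replaces missing responses.
- **The primary result is at risk.** It uses nonresponder imputation and is untouched.

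What remains is that none of the other checks draws on the diary after Week 8 either. The longitudinal model uses scheduled-visit responses, the per-protocol set excludes participants missing Week 12, and the tipping point analysis does not show which scenarios are plausible.

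**Conclusion.** The point holds as an improvement to one sensitivity analysis; it does not correct a demonstrated error. The imputation conditions on less than has been collected, so its missing-at-random assumption is less credible than it could be, and the direction of any bias is unknown in advance. With similar patterns in both arms and 5% to 20% dropout, the treatment difference moves by less than 1 point, apart from 1.3 points for late improvement at 20%. With the pattern in one arm only, it moves by about 1 to 5 points, or roughly 0.2 to 0.7 of a standard error. These sizes rest on assumed dropout rates, variances and autocorrelation, and on dropout after Week 11, which is the timing most favourable to adding the diary weeks. The finding that the added weeks remove the bias in either direction also assumes that dropout depends on itch already recorded in the diary.

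**What to change.** In SAP 7.3.3.3:
- Add the weekly average WI-NRS for Weeks 9, 10 and 11 as auxiliary variables in the fully conditional specification model.
- Use the mean of any one to three final-week entries as a predictor, and define it for participants with a complete window too, since the regression is fitted on them. Imputing the missing days and then averaging, close to the existing Day 7 approach, is an alternative.
- State how ET1 seven-day averages enter the model.
- Record the departure from Protocol 10.4.1 in SAP 11.1.

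Leave the CMH test and the Rubin pooling unchanged.

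The data are already collected, and nothing changes at the sites. Protocol 10.4.1 leaves the details of its sensitivity analyses to the SAP. The cost is SAP wording, a few more correlated variables in the imputation, and the same change for study INCB 18424-320, which the SAP also governs.

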7.3.3.4. Tipping Point Analysis

A tipping point analysis will be conducted to examine the potential effects of missing data. A missing binary response for the primary endpoint in each treatment group will be replaced by a range of values from the most conservative case to the most aggressive case. The most conservative case is that all the missing participants in the ruxolitinib cream group are nonresponders and all the missing participants in the vehicle cream group are responders, while the most aggressive case is the reverse. For each scenario, between-treatment comparisons will be performed using the Fisher exact test.

7.4. Analysis of the Key Secondary Efficacy Parameters

All key secondary efficacy analyses will be conducted on the ITT Population in the DBVC period.

If the primary objective is achieved, the statistical hypotheses for the following key secondary endpoints will be tested in a fixed sequence at a 2-sided $\alpha = 0.05$ level in the following order:

- 1. WI-NRS4 response at Week 4
- 2. Overall-TS at Week 12
- 3. IGA-CPG-S-TS at Week 12
- 4. WI-NRS4 response on Day 7

The statistical comparisons for the key secondary endpoints, WI-NRS4 at Week 4, Overall-TS at Week 12, and IGA-CPG-S-TS at Week 12, will be analyzed using the similar method as specified in the primary analysis. Missing values at each visit will be imputed as nonresponders.

For the composite endpoint Overall-TS, defined as achieving both a WI-NRS4 response and an IGA-CPG-S-TS, the by-visit WI-NRS score (as defined in Section 7.3.1) will be used to derive the Overall-TS response.

For the WI-NRS4 response on Day 7, daily WI-NRS scores will be used for the analysis. Baseline will be defined as the last available daily WI-NRS score during the last week prior to Day 1 (ie, Days −7 to −1). Missing daily WI-NRS scores from Day 1 to Day 7 will be imputed using the similar multiple imputation method as outlined in the sensitivity analysis for the primary endpoint. Specifically, a regression model, including treatment group, stratification factors, baseline daily WI-NRS score, and daily WI-NRS scores from Day 1 to Day 7, will be specified for the fully conditional specification method. For each imputed dataset, the proportion of participant with an WI-NRS4 response on Day 7, defined as a ≥ 4-point improvement (reduction) in daily WI-NRS score from baseline to Day 7, will be analyzed using the CMH test as specified for the primary analysis. Then the results will be combined for inference using Rubin's rule.

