10.4.2. Key Secondary Analysis

Key secondary efficacy analyses will be conducted on the ITT population. If the primary objective is achieved, the statistical comparisons for the key secondary endpoints will be tested in the order specified in Section 10.3.

The key secondary endpoints will be analyzed using the similar method as specified in the primary analysis. Participants with missing WI-NRS scores at Week 4 will be defined as nonresponders for the WI-NRS4 response for that week. Participants missing Week 12 data will be defined as nonresponders for the following endpoints: Overall-TS (both WI-NRS4 response and IGA-CPG-S-TS) at Week 12 and IGA-CPG-S-TS at Week 12.

For WI-NRS4 response on Day 7, missing daily WI-NRS scores from Day 1 to Day 7 will be imputed and analyzed using the similar multiple imputation method as specified in the sensitivity analysis for the primary endpoint.

The summary of key secondary endpoint analyses is provided in Table 15.

Table 15: Summary of Key Secondary Analyses

Parameter	Definition	
Treatment	Ruxolitinib 1.5% cream compared with vehicle cream	
Population	ITT population	
Variable	WI-NRS4 response at Week 4 Overall-TS (WI-NRS4 response and IGA-CPG-S-TS at Week 12) IGA-CPG-S-TS at Week 12 WI-NRS4 response on Day 7	
Population-level summary	Overall odds ration with 95% CI	

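### SAP 7.4 imputes single daily itch scores by regression and then applies the 4-point cut without saying how imputed values return to the 0-10 scale; on the natural reading, imputed participants are called responders too rarely, with a small and conservative effect on the Day 7 result

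*SAP*

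**What the plan says.** SAP 7.2.1 describes the instrument: "The WI-NRS is a PRO comprised of a single item rated on a scale from 0" to 10, recorded each evening "on a scale of 0 to 10 in an eDiary". Neither document says whether the diary accepts only whole numbers.

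For Day 7, SAP 7.4 uses daily scores, not 7-day averages. Baseline is the last available daily score in the week before Day 1, so it too is a single diary entry. Missing scores are imputed by the fully conditional specification method with "a regression model, including treatment group, stratification factors, baseline daily WI-NRS score, and daily WI-NRS scores from Day 1 to Day 7". Response in each imputed dataset is "defined as a ≥ 4-point improvement (reduction) in daily WI-NRS score from baseline to Day 7". A stratified CMH test is run on each dataset and the results are combined by Rubin's rule. Protocol 10.4.2 says only that "missing daily WI-NRS scores from Day 1 to Day 7 will be imputed and analyzed using the similar multiple imputation method" used as a sensitivity analysis for the primary endpoint.

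That sensitivity analysis (SAP 7.3.3.3) imputes 7-day averages and derives the binary response afterwards. Neither document states any rounding, bounds, predictive mean matching or ordinal model for the daily scores.

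Day 7 is last in the fixed sequence (SAP 3.2). It is also the only key secondary endpoint whose main analysis is multiple imputation; the other three count missing values as nonresponse.

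**The concern.** A method suited to a nearly continuous variable has been carried over to a coarse one. The mean of seven whole numbers moves in steps of 1/7, so an unrounded draw cut at 4 is off by at most about half a step, 1/14 or 0.07 points. A single daily score moves in steps of 1, so the half-step is 0.5 points.

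Take a participant with baseline 8 and an imputed Day 7 score of 4.3. The imputed improvement is 3.7, which is scored as failure. The nearest value the diary could have held is 4, which is a response. Recorded participants in effect need about 3.5 on an underlying continuous scale, while imputed participants need 4.0.

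At stake are the accuracy of the Day 7 response rates and their difference on an endpoint in the confirmatory sequence, and of planned Figure 4.1.2.1, the Day 1 to Day 7 curve with multiple imputation. The planned multiple-imputation and tipping-point sensitivity analyses concern only the primary endpoint, so no prespecified analysis would reveal the problem.

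**Working it through.** **Inputs from the documents.** SAP 3.3: "Approximately 180 participants will be randomized 1:1 to ruxolitinib 1.5% cream BID or vehicle cream BID", taken as 90 per arm; the Day 7 row of Table 2 reads "WI-NRS4 response on Day 7 30% 10% > 90" (power in percent); its note specifies Fisher's "exact test, 2-sided α = 0.05". Cut of 4 points and regression imputation: SAP 7.4.

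**Assumptions, because the documents give no figure.** Whole-number diary entries; unrounded normal-regression draws; SD of daily change 1.5 to 3.5 points; 5% to 20% of Day 7 scores missing, at random.

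**1. The plan's own power.** Summing Bin(x1; 90, 0.30) × Bin(x2; 90, 0.10) over all pairs (x1, x2) with a two-sided Fisher p-value of 0.05 or less gives 90.6%. The stated power above 90% reproduces, with little to spare.

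**2. Shortfall among imputed participants.** If a recorded improvement of 4 or more corresponds to an underlying value of at least 3.5, and the true rate is p, the unrounded rule finds P(Z > z_p + 0.5/SD). The ratio to truth is k = P(Z > z_p + 0.5/SD)/p. Example, p = 0.30 and SD = 2: z_p = 0.524, plus 0.25 is 0.774, tail 0.2193, k = 0.731, shortfall 27%.

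| SD | Imputed rate, true 0.30 | Shortfall | Imputed rate, true 0.10 | Shortfall |
|---|---|---|---|---|
| 1.5 | 0.1955 | 35% | 0.0532 | 47% |
| 2.0 | 0.2193 | 27% | 0.0628 | 37% |
| 2.5 | 0.2344 | 22% | 0.0692 | 31% |
| 3.0 | 0.2448 | 18% | 0.0738 | 26% |
| 3.5 | 0.2523 | 16% | 0.0772 | 23% |

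**3. Simulation on the bounded 0-10 scale** (SD 1.5 to 3, between-day correlation 0.5 or 0.8). Unrounded draws gave 24-35% too few responders at a true 30% and 25-46% too few at 10%. Rounding to whole numbers within 0-10 brought the imputed rates to 0.94-1.05 times the truth. Predictive mean matching gave about 29-31% and 10-11%, against true rates of 29-30% and about 10%. At SD 3 rounding recovers only about 0.94 of the truth in the 30% arm, so part of the shortfall there does not come from the cut.

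**4. Effect on the whole arm.** With a share f imputed, the arm rate is p × [1 − f(1 − k)]. Two pairs of ratios are used: 0.72 (ruxolitinib) and 0.62 (vehicle), close to the simulation at SD 2; and 0.75 in both arms.

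| f | k (ruxolitinib, vehicle) | Rates | Difference | Fisher power |
|---|---|---|---|---|
| 0 | none imputed | 30.0%, 10.0% | 20.0 points | 90.6% |
| 5% | 0.72, 0.62 | 29.58%, 9.81% | 19.77 | 90.2% |
| 5% | 0.75, 0.75 | 29.63%, 9.88% | 19.75 | 90.1% |
| 10% | 0.72, 0.62 | 29.16%, 9.62% | 19.54 | 89.9% |
| 10% | 0.75, 0.75 | 29.25%, 9.75% | 19.50 | 89.6% |
| 20% | 0.72, 0.62 | 28.32%, 9.24% | 19.08 | 89.1% |
| 20% | 0.75, 0.75 | 28.50%, 9.50% | 19.00 | 88.5% |

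Over the full SD range in step 2, the understatement f × [0.30(1 − k1) − 0.10(1 − k2)] at f = 10% runs from 0.10 × (0.0477 − 0.0228) = 0.25 points (SD 3.5) to 0.10 × (0.1044 − 0.0468) = 0.58 points (SD 1.5), and is twice that at 20%. The power column treats the lowered rates as ordinary binomials under Fisher's test. The planned analysis is a stratified CMH test pooled over imputations, so the column is a guide to size only.

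**5. Scale against sampling error.** The standard error of the difference is √(0.3×0.7/90 + 0.1×0.9/90) = 5.8 points. A bias of 0.5 points is 0.09 of that, and 1 point is 0.17.

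**The case against.** The strongest reply is that the SAP is silent here, not wrong. It names a regression model within fully conditional specification. It does not prescribe unrounded draws or exclude rounding or predictive mean matching, and it never says diary entries are whole numbers. That is true of the wording, and both points are therefore carried as assumptions. But a programmer who follows section 7.4 literally draws from a regression and applies the cut, and that literal path is the biased one.

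The second reply is size, and it stands. At 10% missing about 9 of 90 participants per arm are imputed. The shortfall is about 9 × 0.30 × 0.28 = 0.8 of a participant on ruxolitinib and 9 × 0.10 × 0.38 = 0.3 on vehicle. Nonresponder imputation, used for the other key secondaries, would at 20% missing cut a 20-point difference to 16, a loss of 4 points against about 1 here. Real-time diary compliance checks, and the site contact one week before the Week 2 visit (close to Day 7), may keep missingness below the range assumed.

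A reader might infer three stronger things that the documents do not support:
- **A threat to Type I error.** The same cut applies in both arms and the difference shrinks toward zero, so the rule does not create a spurious effect.
- **A single figure for the shortfall, such as one quarter.** Any such figure needs an SD of daily change that neither document gives.
- **The same fault in the multiple-imputation sensitivity analysis for the primary endpoint.** That analysis imputes 7-day averages and is much less exposed.

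**Conclusion.** The point holds as a small, correctable bias in how the Day 7 analysis is specified. It rests on whole-number diary entries and unrounded draws, and its size depends on an SD and a missing share that have to be assumed.

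The shortfall is material for the imputed participants themselves (16-35% at a true 30%, 23-47% at 10%) but slight for the trial. The difference is understated by about 0.4-0.5 points at 10% missing with mid-range SDs, and by about 1 point at 20%. Fisher power falls by about one percentage point or less at 10% missing. The direction is conservative. Because Day 7 comes last in the fixed sequence, no other confirmatory test changes. The reason to act is that the rule gives a biased estimate on a confirmatory endpoint and is cheap to correct, not that the trial's conclusions are in danger.

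**What to change.** Add one sentence to SAP 7.4 stating how imputed daily scores are obtained on the 0-10 scale. The preferred wording specifies fully conditional specification with predictive mean matching for the daily scores, including the number of donors, so that every imputed value is an observed scale value. The alternative is to round imputed daily scores to whole numbers within 0-10 before deriving Day 7 response. The sentence should also confirm that the diary accepts only whole numbers. Leave section 7.3.3.3 unchanged.

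The cost is one sentence and one programming option, with no new data. The correction in simulation is close but not exact (step 3). The change should be made before unblinding at the primary database lock so that it remains prespecified. Because the SAP also governs INCB 18424-320, one edit serves both studies.
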